5. STUDY DESIGN

The ‘Simulation-based Arthroscopic Surgery Programme’ MSD-IDREC-2014-152 is a CUREC-approved series of studies investigating the effect of new training methods for our future surgeons and using simulators, cadaver specimens and virtual reality models. These studies involve the assessment of trainee groups (including junior surgical trainees, specialist registrars and consultants) in two ways:

- 1 – on simulators, using metrics such as motion analysis data, global rating scales and participant feedback
- 2 – in theatre, using metrics such as global rating scales, procedure based assessments and participant feedback.

In this particular sub-study, we are recruiting up to 60 junior surgical trainees in T&O posts as part of their training programme. These will all undergo a baseline assessment on an arthroscopic simulator, after which they will be randomised 50:50 to either a control group (regular training i.e. their T&O post) or an experimental group (additional simulation training approx.. 1 hour per week) for the next three months. At 3 months they will undergo repeat assessment on the arthroscopic simulator, and in theatre.

Participants will use simple elbow-worn wireless motion sensors during simulation assessments and simulation training, and during usual training in theatre under consultant-supervision, while the patients received their normal treatment, to assess their effectiveness at monitoring learning and performance in addition to the usual forms of educational monitoring above. Over the course of the study, surgical logbook/training data will be collected by the participant and linked to their other results anonymously.

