7.6. Subsequent Sessions

Those randomised to the experimental group will be asked to attend for 1 hour per week over the next 3 months at the Skills lab in the Nuffield Orthopaedic Centre for regular simulation training. Motion data may also be recorded during these sessions.

At 3 month follow up, all participants will repeat a simulated arthroscopy assessment lasting about 30-45 mins, similar to that which occurred at baseline, and an in theatre assessment using the same wireless elbow sensors. We aim to coordinate these two events in the same visit.

Junior surgical trainees perform surgery under consultant supervision as part of their training programme. It is during one of these surgical cases, we will gather objective surgical motion data in addition to the usual forms of educational evaluation which take place as part of training.

Participants will attend a consultant supervised knee arthroscopy list at the Nuffield Orthopaedic Centre. The participant and consultant will have the wireless sensors attached to their elbows by adhesive tape or custom sleeves that fit to the elbow. They are securely attached to the surgeon's elbows and do not interfere with thorough surgical scrubbing, nor do they interfere with any theatre equipment. The participant will scrub for the case with the consultant. The consultant will perform the procedure the patient has been admitted for, and once complete, will demonstrate a diagnostic knee arthroscopy (a

keyhole video examination of all the structures within the knee) to the participant as per standard surgical training practise. The consultant will then supervise the participant performing the same procedure as would normally happen during surgical training. They will provide the same support, and interrupt the procedure as they would in any other supervised surgical case if they feel this is necessary.

Participants motion analysis parameters will be compared to those of the supervising consultant, which will act as a bench-marking process to account for the technical differences between cases (e.g. the weight or size of the leg). This wireless motion data will be recorded to assess the elbow sensors' effectiveness at monitoring learning and performance in addition to the usual forms of educational monitoring e.g. Procedure-base assessments and global rating scales.

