7.8. Definition of End of Study

The CUREC-approved 'Simulation-Based Arthroscopic Surgery Programme' will allow the repeated practice of technical tasks in a safe environment, whilst posing no risk to patient or learner. Our aim is to assess the effectiveness of simulation based arthroscopic training and to see whether it may have a role in surgical training. More specifically, we will assess the usefulness to training of the new elbow-attached motion sensors during routine, consultant-supervised procedures in theatre.

This research programme will take place over a five year period in the "Oxford Orthopaedic Simulation & Education Centre" which is situated within the Nuffield Department of Orthopaedics, Rheumatology and Musculoskeletal Science. This period expires in 2019.

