8. STATISTICS AND ANALYSIS

8.1. Description of Statistical Methods

Motion analysis data from the elbow-worn wireless motion sensors produces similar data to the wired sensors our group has used previously.

Number of movements and path length are common to both devices. Data distributions will be assessed for normality. Previous studies show such data are not normally distributed and we would expect to use non-parametric tests, in this case the Mann-Whitney U test or Kruskal-Wallis test, to compare performance between groups during a given task. Mann-Whitney U tests will also be used within a group to compare performance before and after training on a simulator.

Surgical logbook data will be assessed using descriptive statistics, and motion analysis performance will be reported with reference to surgical experience.

Questionnaire data regarding the trainee and consultant perception of the utility of these sensors will be reported as descriptive statistics.

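### The planned before/after Mann-Whitney U test within a group is wrong for paired data, and a within-arm change cannot by itself show that simulation training works

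*Combined protocol and SAP*

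**What the plan says.** Section 8.1 plans two kinds of comparison of motion data. The first uses non-parametric tests, "in this case the Mann-Whitney U test or Kruskal-Wallis test, to compare performance between groups during a given task". The second follows directly: "Mann-Whitney U tests will also be used within a group to compare performance before and after training on a simulator".

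The design sections say what lies between the two measurements. Section 5 says of the trainees that "they will be randomised 50:50 to either a control group", which means usual training in their T&O post, or to an "experimental group (additional simulation training approx.. 1 hour per week) for the next three months". Section 7.6 says that at 3 months "all participants will repeat a simulated arthroscopy assessment lasting about 30-45 mins, similar to that which occurred at baseline". The theatre assessment takes place at 3 months only, so only the simulator outcomes have a baseline value.

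On purpose, the objectives in the Synopsis and Section 4 concern the usefulness of the elbow sensors. Section 7.8 adds a programme-level aim: "Our aim is to assess the effectiveness of simulation based arthroscopic training and to see whether it may have a role in surgical training". Its next sentence narrows this to the usefulness of the sensors in theatre.

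The statistics section does not say which comparison is primary, does not define the groups, and gives no adjustment for baseline.

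**The concern.** There are two separate problems in the one sentence.

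**The test does not fit the data.** Mann-Whitney U compares two independent samples. Before and after values on the same trainees are correlated. The test ignores that correlation, so its error rate is not the nominal one and it wastes the precision that pairing gives.

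**The result cannot be attributed to simulation.** Between baseline and follow-up, every trainee in either arm spends three months in a surgical post and then repeats a similar assessment. Section 3 reports that hand movements and path length fall with surgical experience. A change within the experimental arm may therefore reflect ordinary training, repeat-test familiarity, simulation training or any mix of these. The control arm exists to separate them, and a within-arm test makes no use of it. Moving to a paired test cures the first problem but not the second.

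At stake is the programme's statement about simulation. As Section 8.1 stands, a significant before/after result could be reported as a benefit of simulation when simulation added nothing.

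**Working it through.** The plan gives no alpha, power, effect size, SD or correlation, so it has no figure to reproduce. The calculation below is illustrative.

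**From the documents.** "we are recruiting up to 60 junior surgical trainees in T&O posts as part of their training programme", allocated 50:50, gives at most 60 / 2 = 30 per arm. Both arms are measured on the simulator at baseline and 3 months.

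**Assumed.** Two-sided 5% tests; a skewed (lognormal) metric; before/after correlation ρ of 0.3, 0.5 or 0.7; the same gain in both arms of 0, 0.3, 0.5 or 0.8 SD on the log scale; no simulation effect.

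**Check by formula** (normal approximation on the log scale, SD = 1).
- Standard error used by an unpaired test: √(2/30) = 0.258. Its rejection threshold is 1.96 × 0.258 = 0.506.
- True standard error of the paired change: √(2(1−ρ)/30) = 0.183 at ρ = 0.5 and 0.141 at ρ = 0.7.
- No change: 2Φ(−0.506/0.183) = 2Φ(−2.77) = 0.6% at ρ = 0.5; 2Φ(−0.506/0.141) = 2Φ(−3.58) = 0.03% at ρ = 0.7.
- Gain 0.3 SD: Φ((0.3−0.506)/0.183) = 13% at ρ = 0.5; Φ((0.3−0.506)/0.141) = 7% at ρ = 0.7.
- Gain 0.5 SD: Φ((0.5−0.506)/0.183) = 49% at ρ = 0.5; 48% at ρ = 0.7.

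**Simulation** (4,000 studies per setting, 30 per arm, no simulation effect). Percentage of studies significant:

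| ρ | Gain in both arms (SD) | Within-arm Mann-Whitney (as planned) | Within-arm signed-rank | Between-arm Mann-Whitney, 3-month values |
|---|---|---|---|---|
| 0.3 | 0 | 2.1 | 4.8 | 4.4 |
| 0.3 | 0.3 | 15.6 | 26.4 | 4.4 |
| 0.3 | 0.5 | 45.1 | 59.1 | 3.9 |
| 0.3 | 0.8 | 88.2 | 94.1 | 4.0 |
| 0.5 | 0 | 0.6 | 4.4 | 5.0 |
| 0.5 | 0.3 | 13.0 | 34.2 | 5.2 |
| 0.5 | 0.5 | 43.2 | 74.2 | 4.8 |
| 0.5 | 0.8 | 91.4 | 99.1 | 5.0 |
| 0.7 | 0 | 0.2 | 5.7 | 4.8 |
| 0.7 | 0.3 | 8.1 | 50.4 | 4.6 |
| 0.7 | 0.5 | 44.2 | 92.4 | 4.9 |
| 0.7 | 0.8 | 95.1 | 100 | 5.5 |

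A between-arm test on change from baseline gives 4.2-5.2% over the same settings. The simulation agrees with the formula in pattern. It runs a few points lower at 0.5 SD, where the rank test is slightly less efficient than a comparison of means, and a little higher in the extreme tail at ρ = 0.7.

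**Reading the table.**
1. With no change, the planned test rejects in 0.2-0.6% of studies at ρ of 0.5-0.7 (2.1% at 0.3). The signed-rank test holds about 5%.
2. With a shared gain and no simulation effect, the planned test is often significant. The signed-rank test is significant more often still, because the change is real. The error would lie in attributing it to simulation.
3. Only the between-arm comparison stays near 5% throughout.

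**The case against.** The strongest reply is that the randomised comparison is already there. The between-group sentence comes first, and the within-group test is introduced as an addition. An added analysis does not undo randomisation, and the between-arm test keeps its error rate in every setting above. This stands: the plan does not depend on the within-arm test.

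The second reply is that the plan never says the within-group test is its evidence for simulation. The formal objectives concern the sensors. For that purpose, asking whether the sensors register a change over three months is legitimate, and it does not matter what caused the change. This also stands. It is why a correctly paired and correctly labelled within-arm test can stay.

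The third is that the shared gain is assumed. Section 3 makes improvement without simulation training plausible, but no document gives its size over three months. That is correct, and the range is shown for that reason.

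These replies leave a gap. Section 8.1 names neither arm. Kruskal-Wallis is normally used for three or more groups, so the groups could be levels of experience. Section 7.4 provides for analysis blind to allocation, which suggests an arm comparison, but none is specified. The within-group sentence is the only one in Section 8 that mentions training on a simulator, so a reader looking for the test of training would land on it. None of the replies touches the pairing error.

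**Conclusion.** The point holds in two parts. The pairing error is definite: Mann-Whitney U is the wrong test for before/after values on the same trainees. With 30 trainees and an assumed correlation of 0.5-0.7, it rejects in under 1% of studies when nothing changes.

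The attribution problem follows from the design. Its size is conditional: with an assumed shared gain and no simulation effect, the planned within-arm test is significant in about 43-44% of studies at 0.5 SD and 8-13% at 0.3 SD (correlation 0.5-0.7), against about 5% between arms. These figures take the maximum recruitment of 60.

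Three stronger readings go beyond the documents:
- A reader might infer that the plan rests its case for simulation on the within-arm test. It does not say so, and it plans a between-group comparison as well.
- A reader might take it as established that trainees would improve anyway. That is an inference from Section 3, of unstated size.
- A reader might infer that significance in one arm will be set against non-significance in the other. No section proposes this.

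The plan should be corrected before analysis, but the flaw does not invalidate the randomised comparison.

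**What to change.** Replace the within-group sentence in Section 8.1 with:

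> The effect of simulation training is judged by the comparison between the randomised arms at 3 months, adjusted for the baseline simulator value for simulator outcomes. Within-arm change is reported for both arms as the median paired change with 95% CI; any test of it uses a paired method (Wilcoxon signed-rank), is descriptive of whether the sensors register change, and is not described as an effect of simulation training.

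This needs no new data, since the baseline simulator values are already collected under Section 7.3.

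The cost is that within-arm p-values can no longer be quoted as evidence for simulation, so that conclusion rests on a comparison of limited power. With 30 per arm and a true effect of an assumed 0.5 SD, the unadjusted between-arm Mann-Whitney test has power of about 44% (49% by normal approximation). Baseline adjustment recovers part of this, because it multiplies the variance by 1−ρ². By normal approximation, power = Φ(0.5/√(1−ρ²) × √(30/2) − 1.96), which is Φ(2.24 − 1.96) = 61% at ρ = 0.5 and Φ(2.71 − 1.96) = 77% at ρ = 0.7.

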8.2. The Number of Participants

We plan to use these elbow-worn wireless motion sensors during as an additional educational monitoring tool during normal surgical training. We have not set a limit on the participant numbers (although up to 60 participants per year is possible). More participants to the studies within 'Simulation-based Arthroscopic Surgery Programme' at all stages will allow us to monitor their performance and develop performance curves, to show how motion analysis parameters change with surgical experience.

9. DATA MANAGEMENT

9.1. Access to Data

Direct access will be granted to authorised representatives from the Sponsor and host institution for monitoring and/or audit of the study to ensure compliance with regulations.

OSEC research team members will have access to raw motion data, and output metrics generated from the raw data. By unique identifiers, this can be matched to other metrics during the Simulation-based Arthroscopic Surgery Programme, but not de-anonymised to reveal participants or patients.

Our collaborator computer at MAT will have access to the raw motion data, and use this to produce algorithms to generate the performance output metrics. They will not require access to any files that matches participants to their unique identifiers, nor to non-motion sensor data generated by participants elsewhere in the study. As such, MAT computer scientists will not be able to link any motion data to participants.

9.2. Data Recording and Record Keeping

Anonymised non-personal raw motion data will be uploaded to secure off-site servers using SSL/TLS using strong cipher suites that support perfect forward secrecy. This prevents decoding of captured data, even if the secret long-term key itself is compromised. Every instance has a built in firewall that is configured using a least privilege basis and will only accept https (port 443) connections from the

internet. The data centres are staffed 24x7 by trained security guards and access is authorised strictly on a least privileged basis.

This data will remain anonymised regarding the participant, and will contain no information related to patients. The raw motion data can be queried to generate usable motion analysis metrics (e.g. smoothness, hand movements etc). These are not stored on the server, but generated on request via proprietary algorithms. Pooled anonymised non-personal raw data from participants' motion data is used to generate and refine the algorithms, and as such, as more raw data is acquired by the server, the requested outputs become more accurate. Pooled data cannot be extracted to be attributed to any participant.

Usable output motion analysis metrics will be downloaded from the server and stored locally on an Excel spreadsheet (.xlsx). These data may be opened in other programmes or copied to other formats for certain analyses e.g. SPSS data files (.sav). Where study data are generated in a proprietary file type, these will be transposed to Excel format.

The participants will be identified by a unique study specific number and/or code in any database. The name and any other identifying detail will NOT be included in any study data electronic file. All study data files will be kept on password protected hard-drives. Output study data will be kept for a further 3 years following the completion of the study before being destroyed. Anonymised non-personal raw data from the sensors will contribute to the algorithm on the secure server, but will not be extractable or identifiable to any participant.

10. QUALITY ASSURANCE PROCEDURES

The study will be conducted in accordance with the current approved protocol, GCP, relevant regulations and standard operating procedures, may be monitored, or audited against these.

11. ETHICAL AND REGULATORY CONSIDERATIONS

11.1. Declaration of Helsinki

The Investigator will ensure that this study is conducted in accordance with the principles of the Declaration of Helsinki.

11.2. Guidelines for Good Clinical Practice

The Investigator will ensure that this study is conducted in accordance with relevant regulations and with Good Clinical Practice.

11.3. Approvals

The protocol, informed consent form, participant information sheet and any proposed advertising material will be submitted to an appropriate Research Ethics Committee (REC), and host institution(s) for written approval.

The Investigator will submit and, where necessary, obtain approval from the above parties for all substantial amendments to the original approved documents.

11.4. Reporting

The CI shall submit once a year throughout the study, or on request, an Annual Progress report to the REC Committee, host organisation and Sponsor. In addition, an End of Study notification and final report will be submitted to the same parties.

11.5. Participant Confidentiality

The study staff will ensure that the participants' anonymity is maintained. The participants will be identified only by a participant ID number on all study documents and any electronic database, with the exception of the CRF, where participant initials may be added. All documents will be stored securely and only accessible by study staff and authorised personnel. The study will comply with the Data Protection Act, which requires data to be anonymised as soon as it is practical to do so.

11.6. Expenses and Benefits

No payments are intended for the participants. Participants may receive benefit from access to simulation training, and any technical skills development that may result.

11.7. Other Ethical Considerations

The aims of this project are to develop a novel method of educational monitoring: some monitoring will take place in a patient setting (the operating theatre), but does not involve the alteration of patient treatment.

The wireless sensors are safe to use in a clinical environment. They are securely attached to the surgeon's elbows and do not interfere with thorough surgical scrubbing, nor do they interfere with any theatre equipment. They do not make contact with the patient, and are not attached or implanted in the patient. They do not involve the collection of any patient identifiable data, nor storage of tissue samples. As such, they pose no risk or interruption to standard theatre procedure.

The methods of assessing technical skills being investigated by these studies are experimental. As such, these will not be used to draw conclusions about a trainee's performance with regards to the requirements of the training programme, and will not be available to the Deanery for ARCP evaluations.

So as participants randomised to the control group are not disadvantaged in terms of training opportunities, they will be offered the simulation training experience by the experimental group free of charge when they have completed their participation in the study.

12. FINANCE AND INSURANCE

12.1. Funding

Dinwoodie Simulation Research Fellowship funded by Royal College of Surgeons of England

NIHR Oxford Musculoskeletal Biomedical Research Unit

12.2. Insurance

The University has a specialist insurance policy in place which would operate in the event of any participant suffering harm as a result of their involvement in the research (Newline Underwriting Management Ltd, at Lloyd's of London). NHS indemnity operates in respect of the clinical treatment that is provided.

13. PUBLICATION POLICY

The Investigators will be involved in reviewing drafts of the manuscripts, abstracts, press releases and any other publications arising from the study. Authors will acknowledge that the study was funded by Royal College of Surgeons of England Dinwoodie Research Fellowship and NIHR Oxford Musculoskeletal Biomedical Research Unit. Authorship will be determined in accordance with the ICMJE guidelines and other contributors will be acknowledged.

The Investigators will be involved in reviewing drafts of the manuscripts, abstracts, press releases and any other publications arising from the study. Authors will acknowledge that the study was funded by NIHR Oxford Musculoskeletal Biomedical Research Unit. Authorship will be determined in accordance with the ICMJE guidelines and other contributors will be acknowledged. The findings will also be used towards a DPhil thesis for [name].

Participants will be alerted to publication of findings via email.

14. APPENDIX C: AMENDMENT HISTORY

Amendment No.	Protocol Version No.	Date issued	Author(s) of changes	Details of Changes made
1	1.0	26 June 2015	[name]	Use of McLaren Server to store anonymous data generated from motion sensors; retain data at end of project
2	1.0	31 July 2015	[name]	Elbow sensors added (as technically Class B Invasive, being attached to participant)
3	1.0	5 Nov 2015	[name]	Additional consent for study data in future studies; consent for logbook data; change in population to junior orthopaedic trainees
4	1.0	16 Nov 2015	[name]	Clarification of aspects of Simulation Based Arthroscopic Surgery programme relevant to this study (previously only mentioned theatre)
